# 7.2. Patient Exclusion Criteria

Any patient who meets any of the following criteria (in any eye) will not qualify for entry into the study:

#### Ocular

- 1. CFS score ≥4 on a modified Oxford scale
- 2. Ocular hypertension or glaucoma requiring IOP-lowering medication(s)
- 3. History of ocular trauma, infection or ocular inflammatory condition within the last 3 months before the screening visit.
- 4. Severe blepharitis and/or severe meibomian gland disease
- 5. Filamentary keratitis
- 6. Any ocular surface anomaly not related to DED
- 7. Active ocular infection or history of ocular allergy or ocular herpes
- 8. Patient with only one sighted eye or with a best corrected distance visual acuity  $\leq 1/10$
- 9. Use of any topical ocular treatment other than study device during the study (all non-study topical ocular treatment(s) must be stopped at the screening visit)
- 10. Onset of lid hygiene (whatever the method) less than 2 months before the Screening visit
- 11. Use of topical corticosteroids one month before the Screening Visit

- 12. Use of isotretinoin, ciclosporin, tacrolimus, sirolimus, pimecrolimus or ocular cauterisation procedures 2 months before the screening visit and throughout the study
- 13. Use of VISMED® within 6 weeks prior to the screening visit
- 14. Refractive surgery (e.g. LASIK, LASEK, PRK) within 6 months and/or any other ocular laser/surgery within 3 months prior to the screening visit and during the study
- 15. Insertion of temporary punctal plug(s) within 2 months prior to the Screening visit or permanent occlusion of lacrimal puncta on one or both sides
- 16. Known hypersensitivity to any of the components of the study device or investigational products

#### Non-ocular

- 17. History of severe systemic allergy
- 18. Systemic disease not stabilised within 1 month prior to the screening visit (e.g. diabetes with glycaemia out of range, thyroid dysfunction) or judged by the investigator to be incompatible with the conduct of the study procedures or the interpretation of the study results
- 19. Any change of systemic concomitant medication within the month before the screening visit or planned change during the study period, except paracetamol
- 20. Pregnancy or lactation at the screening and/or Baseline visit.
- 21. Women of childbearing potential not using a medically acceptable, highly effective method of birth control (such as hormonal implants, injectable or oral contraceptives together with condoms, some intrauterine devices, sexual abstinence or vasectomised partner) from the Baseline visit throughout the conduct of the study treatment periods and up to 2 weeks after the study end. Post-menopausal women (two years without menstruation) do not need to use any method of birth control.
- 22. Participation in a clinical trial with an investigational substance within the past 30 days prior to Baseline visit.
- 23. Participation in another clinical study at the same time as the present study.

## 7.3. Screen Failure

Investigators must account for all patients who sign the informed consent form. If the patient is found to be not eligible at the Baseline Visit after signing the informed consent, the investigator should complete the eCRF to record the primary reason of failure.

Patient numbers assigned to patients who fail eligibility assessments should not be reused.

Re-assessment is possible. Patients may undergo a new Baseline visit after the signature of a new informed consent form, and a new patient number will be assigned.

#### 7.4. Patient Discontinuation or Withdrawal Criteria

The primary reason for discontinuation or withdrawal of a patient from the study should be recorded in the electronic case report form (eCRF) using the following categories:

## 1. Adverse event (AE).

The patient experiences an AE that requires early termination because continued participation imposes an unacceptable risk to the patient's health or the patient is unwilling to continue because of an AE. Patients discontinued for device-related AE(s) will be followed-up after patient's discontinuation until the effect is resolved, stabilized or a final assessment can otherwise be done by the investigator.

#### 2 Protocol deviation

The discovery after the administration of the first dose of the study device that the patient failed to meet protocol entry criteria or that the patient did not adhere to protocol requirements, and continued participation poses an unacceptable risk to the patient's health.

# 3. Lost to follow-up.

The patient does not return to the clinic and attempts to contact the patient are unsuccessful. In case of a patient lost-to-follow-up, the investigator must do his/her best to contact the patient initially by phone, then by letter, and finally by certified mail. If no response is obtained from the patient, the investigator is encouraged to contact one of the patient's relatives or his/her general physician. These attempts must be documented and associated documentation filed in the patient medical chart.

## 4. Voluntary withdrawal.

The patient (or patient's legally acceptable representative) wishes to withdraw from the study. The reason for withdrawal, if provided, should be recorded in the eCRF.

Note: All attempts should be made to determine the underlying reason for the withdrawal and, where possible, the primary underlying reason should be recorded (i.e., withdrawal due to an AE should not be recorded in the "voluntary withdrawal" category).

#### 5. Study termination.

The Sponsor, EC, or regulatory agency terminates the study.

#### 6. Lack of efficacy.

The patient or the physician does not feel that the study device has adequately relieved his/her patient's symptoms.

# 7. Pregnancy.

The patient is found to be pregnant.

Note: If the patient is found to be pregnant, the patient must be withdrawn immediately. The procedure is described in Section 7.5.

- 8. Investigator decision due to non-compliance (to study devices, study visits or study related procedure).
- 9. Other reason, specify.

Note: All attempts should be made to determine the reason if Other is chosen (e.g. a patient moves to another part of the country, or to a different country, and can no longer be traced) and the specific primary reason should be recorded in the "specify" field of the eCRF.

# 7.5. Procedures for Discontinuation or Withdrawal of a Patient

The investigator may terminate a patient's study participation at any time during the study when the patient meets one or more of the study withdrawal criteria described in Section 7.4. Efforts should be made to perform all procedures scheduled for the End of Study Visit (D84/End of treatment). Discontinued patients will not be replaced.

# 7.6. Completed Enrollment

The study enrolment will be considered as completed when the desired number of at least 80 included patients is reached.

# 7.7. Concomitant Medications/Therapies

Concomitant therapies consist of any treatment or medication given concurrently with the study devices. The following concomitant medication(s)/treatment(s) are prohibited during study participation:

- Use of any artificial tears other than those provided by the Sponsor during the screening period.
- Use of any artificial tears after the Baseline visit
- Use of any topical ocular treatments other than the study devices and preservative-free IOP lowering agents.
- Insertion of temporary punctal plugs during the study.
- Use of any topical corticosteroids after the Baseline visit
- Use of any isotretinoin, ciclosporin, tacrolimus, sirolimus, pimecrolimus or ocular cauterisation procedures after the Baseline visit

The initiation or use during the course of the study of any treatments or procedures described above will be considered as a protocol deviation.

# 7.8. Randomisation and Masking

The patients who fulfil the inclusion criteria will be randomly assigned (by IWRS/IVRS) in a 1:1 ratio to receive either ALOCROSS® or VISMED® for 12 weeks (84 days) in an investigator-masked fashion.

Each randomised patient will receive numbered study device kits as assigned by the system.

Treatment assignments will be masked to Santen and ITEC employees (except for the Drug Supply personnel), and Investigators. The investigator should try to avoid breaking the masking codes. However, IN CASE OF EMERGENCY ONLY, (i.e. SERIOUS ADVERSE EVENT [SAE]

AND ONLY WHEN THIS INFORMATION INFLUENCES THE MANAGEMENT OF THE PATIENT CARE), the investigator is entitled to unmask the patient by using IWRS, in order to obtain the study device information (i.e. ALOCROSS® or VISMED®) to immediately start the appropriate treatment [to be recorded in the source data and eCRF (electronic Case Report Form)]. The date, time and reason for breaking the code will be recorded. The investigator should inform the Sponsor immediately after unmasking. The details of this unmasking procedure will be described in a separate document. Patients unmasked for the management of a SAE will be discontinued from the study.

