#### 8.2.2. Study device

At the Baseline visit (V2), after confirmation of fulfilment of the inclusion criteria and randomisation, the patient will be provided with the study devices (i.e. ALOCROSS® or VISMED®) (see Figure 2)

[figure not shown]
The study devices will be supplied in double-masked polyethylene single-dose unit (SDU) containers presented

- in sealed laminate aluminium pouch package (1 pouch contains 5 single-dose unit containers, sufficient for a one-day treatment of both eyes daily pouch).
- 7 aluminium pouches (i.e. 35 single-dose unit containers, sufficient for a one-week treatment) will be placed together in a small cardboard box weekly box.
- 4 cardboard boxes of 7 aluminium pouches (i.e. 140 SDU of study device, sufficient for a 4-week treatment) will be placed together in a large sealed cardboard box monthly box.

One 'monthly' box of 140 SDU will be dispensed at the Baseline visit.

Two 'monthly' boxes of 140 SDU will be dispensed at the D28 visit.

Figure 2: Study device packaging

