## 8.2.3. Labelling

The single dose containers will not be labelled.

- VISMED® single dose unit containers will receive a blank green sticker to mask the commercial device name.
- ALOCROSS® single dose unit containers will receive a blank white sticker to mask the commercial device name.

Each aluminium pouch and sealed cardboard will bear an investigational label, indicating that the content is intended for investigational use only, the treatment number and the weekday (Monday, Tuesday, ...).

In addition, each large cardboard box will bear a white detachable label bearing the protocol and treatment numbers. This label will be torn off by the person dispensing the study device to the patient on Day 1, and stuck onto the space provided in the accountability log.

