# **8.6.** Treatment Compliance

Patient compliance will be assessed at each visit by the investigator's unmasked designee by questioning the patient and comparing to study device accountability. All reported lack of compliance will be recorded on the eCRF with the reasons. If a patient is persistently non compliant with the study device, the patient should be withdrawn from the study. All patients should be reinstructed about the dosing requirement at each study visit. The authorized unmasked study personnel conducting the re-education must document the process in the patient source records

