# 10.4. Symptoms of ocular discomfort – Visual analogue scale

The visual analogue scale is a self-administered questionnaire and must be completed by the patient him/herself.

Itching, foreign body sensation or sandy feeling or grittiness, photophobia, burning/stinging, eye dryness, pain or ocular discomfort and sticky feeling will be assessed by the study patients using a visual analog scale from no discomfort to maximal discomfort (0 to 100%). Symptoms will be evaluated for both eyes together. (see Appendix A-III Visual Analog Scale (VAS)\_Symptoms of Ocular Discomfort).

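### Section 7.8 does not list the patient as masked although the units hide the product name, and sticker colour codes the arm: an avoidable bias risk that is cheap to reduce

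*Protocol*

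**What the plan says.** Section 7.8 randomises patients "to receive either ALOCROSS® or VISMED® for 12 weeks (84 days) in an investigator-masked fashion" and then lists who is masked: "Treatment assignments will be masked to Santen and ITEC employees (except for the Drug Supply personnel), and Investigators". The patient does not appear in that list.

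The supply sections describe something closer to concealment from the patient as well. Section 8.2.2: "The study devices will be supplied in double-masked polyethylene single-dose unit (SDU) containers". Section 8.2.3 leaves the single-dose units without a product label and hides the brand on each: "VISMED® single dose unit containers will receive a blank green sticker to mask the commercial device name" and "ALOCROSS® single dose unit containers will receive a blank white sticker to mask the commercial device name". Pouches and boxes carry an investigational label with a treatment number and weekday.

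Under section 8.6, the investigator's unmasked designee questions the patient on compliance at each visit, and patients are reinstructed on the dosing requirement. "The authorized unmasked study personnel conducting the re-education must document the process in the patient source records". Section 8.5 has patients bring unused containers to each clinic visit.

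Several outcomes come from the patient. For symptoms, section 10.4 says: "The visual analogue scale is a self-administered questionnaire and must be completed by the patient". The patient also gives a global efficacy rating (10.6) and completes the NEI-VFQ-25 (10.5). Section 5.3.2.1 lists symptom change and the patient's subjective assessments as secondary endpoints. Section 12.5.2 compares the symptom VAS between arms by MMRM and treats the NEI-VFQ-25 as exploratory. The primary endpoint (5.3.1) is the staining score, graded at the slit lamp.

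**The concern.** Sections 7.8 and 8.2 do not agree on who is kept from knowing the product. The packaging hides the brand from the person who handles the units every day, but the masking section gives that person no masked status, and no instruction to staff or patients follows from the packaging.

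Two routes to bias stay open.

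- **Direct.** A patient who learns whether the drops are the new product or an established comparator may rate symptoms, global efficacy or quality of life differently. The unmasked designee speaks to the patient about the device at every visit, and the protocol does not tell that person to withhold the name.
- **By relay.** The examiner grades the primary staining score and gives the investigator's global rating. A patient who knows the product could mention it. The patient need not know it, however. Section 8.2.3 prints the colour code in the protocol that the investigator works from, so a remark about the sticker colour, or the sight of a returned unit, could be enough.

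In a non-inferiority trial, a bias that favours the test product makes the margin easier to meet. A bias against it costs power.

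**Working it through.** **1. The plan's own figure.** Inputs from section 12.1.1: SD 2.5, margin 2, one-sided alpha 0.025, power 90%; a true difference of 0 is assumed.

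n per arm = 2 × (1.960 + 1.282)² × 2.5² / 2² = 32.8, so 33 per arm and 66 in total. This reproduces the stated 66. Allowing 15% exclusions, 66 / 0.85 = 77.6, so 78; the planned 80 covers it (80 × 0.85 = 68). Masking the patient changes none of these figures.

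**2. The sections side by side.**

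| Question | Where | What is there |
|---|---|---|
| Is the patient listed as masked? | 7.8 | No |
| Is the product name hidden on the unit? | 8.2.2, 8.2.3 | Yes, both products |
| Is the arm hidden on the unit? | 8.2.3 | No: green against white |
| Are patients told their product? | No section says so | Not stated |
| Are unmasked staff barred from naming it? | 8.5, 8.6 | Not stated |
| Are patients told not to discuss or show units to the examiner? | 8.5, 9.1 to 9.5 | Not stated |

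**3. Symptom VAS, illustration only.** The protocol gives no SD for the VAS and no expectation effect. Assume an SD of 20 mm and an effect of 2 to 10 mm.

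- 34 per arm (80 × 0.85 / 2): SE = 20 × √(2/34) = 4.85 mm. The assumed effect is 2/4.85 = 0.41 to 10/4.85 = 2.06 SE.
- 40 per arm (all randomised patients in the full analysis set): SE = 20 × √(2/40) = 4.47 mm. The assumed effect is 0.45 to 2.24 SE.

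These ratios only restate the assumptions on the scale of the trial's precision.

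**4. Primary staining score by relay, illustration only.** SE = 2.5 × √(2/33) = 0.615 points. Let b be a bias in the difference between arms. The protocol gives no value for b.

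- One-sided error when the true difference is 2 and b favours the test arm: Φ(b/SE − 1.960).
- Power when the true difference is 0 and b is against the test arm: Φ((2 − b)/SE − 1.960).

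| Assumed b (points) | Error at the margin | Power |
|---|---|---|
| 0 | 0.025 | 0.90 |
| 0.25 | 0.060 | 0.81 |
| 0.5 | 0.126 | 0.68 |
| 1.0 | 0.369 | 0.37 |

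Here b is the average shift over all patients in the comparison. If only some patients relay the product, the shift in those patients' scores would have to be correspondingly larger.

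**The case against.** Investigator-masking is a declared design choice. The title, the synopsis and sections 6.1 and 7.8 all use it, and it covers the person who grades the primary endpoint. Sending accountability and compliance through an unmasked designee is a safeguard for that examiner. The name is in fact concealed on every unit dispensed, so the gap lies in wording and instructions more than in supply. All of this stands.

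Four stronger readings are tempting, and the documents do not support them.

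- *Patients know their product.* No section says that they are told. The consent text, which might settle it, was not available. The harm is argued from silence in both directions.
- *The examiner is effectively unmasked.* Relay needs a patient to mention or show something. The colour code makes that easier but does not make it happen, and the units are packed in sealed pouches and boxes.
- *The primary analysis has an inflated error rate.* The figures above depend on a bias that nobody has measured, in a direction that nobody knows.
- *The packaging already masks the patient, so wording alone completes the job.* The name is hidden but the arm is colour-coded. Section 8.1.2 calls VISMED commonly used in France, and section 7.2 excludes only use within 6 weeks before screening, so an earlier user might recognise the container or the drop.

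The reach is also limited. The NEI-VFQ-25 analysis is exploratory. Section 12.5.2 specifies a between-group test for the investigator's global rating but none for the patient's.

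**Conclusion.** The point holds as an avoidable weakness in conduct. It is not a calculation error and not a flaw in the choice of an investigator-masked design. Section 7.8 and section 8.2 need to be reconciled, and the protocol lacks the instructions that would make use of the concealment it already supplies. The exposure is direct for the symptom VAS, the patient global rating and the NEI-VFQ-25, and arises only by relay for the primary staining score.

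The size of the bias is unknown. If the assumed SD of 20 mm is near the truth, an expectation effect of a few millimetres would be a noticeable fraction of the standard error of the VAS comparison. For the primary endpoint, an average relay bias of 0.25 to 0.5 points would matter, but the documents give no reason to expect that amount. The case for acting rests on the low cost of the change, not on a demonstrated effect.

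**What to change.** - In section 7.8, state that patients are not told the product name, so that it agrees with section 8.2.2.
- In sections 8.5 and 8.6, require the unmasked designee not to name or show the commercial product or its leaflet to the patient.
- In section 8.5 or 9, instruct patients not to discuss their product with the examiner or show the examiner their units, and to hand returned containers only to the unmasked designee.
- In section 8.2.3, use the same sticker colour on both products.
- Keep the label investigator-masked. Patients may still recognise the container or the feel of the drop, so a claim of full patient masking would go too far.

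The cost is protocol wording, a line in site training and a minor sticker change; it is larger if units have already been stickered, which the protocol does not say. Sample size, alpha, margin and visits stay as they are. Patient masking will remain imperfect.

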## 8. STUDY DEVICE MATERIALS AND MANAGEMENT

# 8.1. Study Devices

# 8.1.1. Description of tested device, ALOCROSS®

ALOCROSS® is class IIb medical device and is a lubricant ophthalmic solution based on cross-linked hyaluronic acid 0,20% and Aloe vera gel 0,10% in a buffered solution at pH 7.2.

The batch number and the expiration dates of the study device will be provided in the certificate of analysis.

The legal manufacturer will be OFF Health located in Florence, Italy.

# 8.1.2. Description of reference treatment, VISMED®

VISMED® is a sterile medical device that contains a preservative-free, drug-free solution of sodium hyaluronate at 0.18%. VISMED® is commonly used as a preservative-free artificial tear treatment in France for patients with keratitis or keratoconjunctivitis. VISMED® will be purchased from a commercial source.

# 8.1.3. Description of artificial tears, LARMABAK®

LARMABAK® is a sterile unpreserved solution for topical ophthalmic use, containing NaCl at 0.9% (0.9 g/100 mL). LARMABAK® will be purchased from a commercial source.

# 8.2. Study Device Packaging and Labelling

## 8.2.1. $LARMABAK^{\mathbb{R}}$

At the screening visit and after review of the selection criteria, selected patients will be provided with 1 bottle of LARMABAK® to perform the wash-out treatment period.

**Dosage and mode of administration of LARMABAK®**: Instillation of one drop into both eyes, 4 times and up to 8 times daily.

 $LARMABAK^{\textcircled{\$}}$  bottles will bear an investigational label to indicate that the content is intended for investigational use only and to allocate a treatment number to the unit.

#### 8.2.2. Study device

At the Baseline visit (V2), after confirmation of fulfilment of the inclusion criteria and randomisation, the patient will be provided with the study devices (i.e. ALOCROSS® or VISMED®) (see Figure 2)

[figure not shown]
The study devices will be supplied in double-masked polyethylene single-dose unit (SDU) containers presented

- in sealed laminate aluminium pouch package (1 pouch contains 5 single-dose unit containers, sufficient for a one-day treatment of both eyes daily pouch).
- 7 aluminium pouches (i.e. 35 single-dose unit containers, sufficient for a one-week treatment) will be placed together in a small cardboard box weekly box.
- 4 cardboard boxes of 7 aluminium pouches (i.e. 140 SDU of study device, sufficient for a 4-week treatment) will be placed together in a large sealed cardboard box monthly box.

One 'monthly' box of 140 SDU will be dispensed at the Baseline visit.

Two 'monthly' boxes of 140 SDU will be dispensed at the D28 visit.

Figure 2: Study device packaging

## 8.2.3. Labelling

The single dose containers will not be labelled.

- VISMED® single dose unit containers will receive a blank green sticker to mask the commercial device name.
- ALOCROSS® single dose unit containers will receive a blank white sticker to mask the commercial device name.

Each aluminium pouch and sealed cardboard will bear an investigational label, indicating that the content is intended for investigational use only, the treatment number and the weekday (Monday, Tuesday, ...).

In addition, each large cardboard box will bear a white detachable label bearing the protocol and treatment numbers. This label will be torn off by the person dispensing the study device to the patient on Day 1, and stuck onto the space provided in the accountability log.

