# 8.5. Study Device Accountability and Destruction

The Principal Investigator has overall responsibility for ensuring that an inventory is conducted upon receipt of the clinical supplies. Due to the study being Investigator Masked, all study device accountability and destruction must be undertaken by the Investigator's unmasked designee. The receipt of clinical supplies should be completed, signed and returned as directed by Santen (or designee). A copy must be maintained at the site for the Investigator's records. The Principal Investigator's unmasked designee will keep a current record of the inventory and dispensing of all study devices. This record will be made available to Santen's Un-masked Monitor (or designee) for the purpose of accounting for all clinical supplies. Any discrepancy and/or deficiency must be recorded with an explanation. All supplies sent to investigator must be accounted for and in no case will study device be used in any unauthorised situation.

It is a responsibility of the Principal Investigator to return any unused supplies to the Santen Unmasked monitor (or designee) at the conclusion of the study.

Patients will be instructed to keep all unused, expired or malfunctioning containers (bottle, SDU and box) and will be required to bring unused, expired or malfunctioning study device containers to each clinic visit. The destruction of the unused, expired or malfunctioning containers of study device will be performed according to the instructions of the clinical monitor and has to be documented.

Upon completion or earlier termination of the study the investigator's unmasked designee will, unless otherwise agreed, return to the clinical supplies distributor any surplus quantities, unused containers/bottles/SDU, of study device or unpreserved artificial tears. The investigator's unmasked designee will record each quantity of study device or unpreserved artificial tears that has been damaged or is missing.

Study device supplies will be counted and reconciled at the site before being returned to Santen or designee or being destroyed by the site.

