## 9. SCHEDULE OF OBSERVATIONS AND PROCEDURES

The schedule for all study-related procedures and evaluations is shown in Table 3. Assessments should be completed at the designated visit/time point(s), and should be performed in both eyes.

All assessments should be done in the mentioned order to ensure that additional procedure doesn't interfere with the results of other examinations.

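### Section 8.2.3 gives each arm its own sticker colour and prints the key, so one unit seen out of its pouch unmasks the investigator

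*Protocol*

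**What the plan says.** Section 8.2.3 of the protocol fixes the sticker by arm: "VISMED® single dose unit containers will receive a blank green sticker to mask the commercial device name", and "ALOCROSS® single dose unit containers will receive a blank white sticker to mask the commercial device name". The pouches and boxes around the units carry a treatment number and a weekday, and no difference between arms is described for them. Section 8.2.2 calls the unit containers double-masked and sets the pack size: "1 pouch contains 5 single-dose unit containers, sufficient for a one-day treatment of both eyes".

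On who is masked, section 7.8 says "Treatment assignments will be masked to Santen and ITEC employees (except for the Drug Supply personnel), and Investigators".

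Three provisions keep the examiner away from the units:
- Section 8.5: "all study device accountability and destruction must be undertaken by the Investigator's unmasked designee".
- Section 8.6: "Patient compliance will be assessed at each visit by the investigator's unmasked designee by questioning the patient and comparing to study device accountability".
- Section 9: "All assessments should be done in the mentioned order". Sections 9.3 to 9.5 list staining before the compliance check and, at Days 28 and 84, before container collection.

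Section 8.5 also brings the units into the clinic, since patients "will be required to bring unused, expired or malfunctioning study device containers to each clinic visit".

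**The concern.** There are two arms and one colour per arm, so the colour of a single unit identifies the allocation with certainty to anyone who has read 8.2.3. The stickers remove a brand name and put an arm code in its place.

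This matters because the efficacy outcomes most exposed are matters of judgement. The primary endpoint is an examiner's grade on an ordinal staining scale read at the slit lamp (10.1), and no independent reader is described. The global efficacy rating is expressly the investigator's (10.6) and is compared between groups at weeks 2, 4 and 12 (12.5.2). If the grader knows the arm, the planned analysis can neither detect nor remove the resulting bias. Investigator masking is the protection that the trial claims in its title.

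**Working it through.** **1. Does the colour reveal the arm?** Sections 8.2.3 and 7.8 side by side: green means VISMED, white means ALOCROSS, and the investigators who must not know the arm hold the document that says so. The sticker is on the unit inside the pouch, so any unit out of its pouch is enough, opened or not.

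**2. Do the safeguards close the gap?**
- *Sealed outer packaging* protects stored and dispensed stock. It does not protect units taken out of a pouch by the patient.
- *The unmasked designee* covers accountability, destruction and compliance. Sections 8.3 and 8.4, however, give handling and dispensing to the investigator or a designee without requiring that person to be unmasked, and one sentence in 8.5 makes the Principal Investigator responsible for returning unused supplies.
- *The visit order* separates staining from container handling at the same visit only. A colour seen or mentioned at Day 14 is still known at Day 28. Adverse-event recording is listed before staining (9.3 to 9.5) and uses an open question (11.2.1.1), so a patient may mention the drops before grading.
- *The investigator's global rating* gets no protection from the order. It is listed after the compliance check at all three follow-up visits and after container collection at Days 28 and 84.

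**3. How many loose units could be in circulation?**

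Inputs: 5 units per pouch and 7 pouches per weekly box; 4 weekly boxes per monthly box; one monthly box at baseline and two at Day 28 (8.2.2); 4 instillations a day (8.4).

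The protocol's pack sizes reproduce: 5 × 7 = 35, 35 × 4 = 140, 2 × 140 = 280.

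Assumptions: full compliance, visits on time (14, 28 and 56 days of use), and one unit per instillation for both eyes. One unit per eye would need 8 a day, more than the 5 that 8.2.2 calls sufficient.

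| Visit | Units used | New pouch each day | Spares used first |
|---|---|---|---|
| Day 14 | 4 × 14 = 56 | 5 × 14 − 56 = 14 | 12 pouches: 60 − 56 = 4 |
| Day 28 | 4 × 28 = 112 | 140 − 112 = 28 | 23 pouches: 115 − 112 = 3 |
| Day 84 (second supply) | 4 × 56 = 224 | 280 − 224 = 56 | 45 pouches: 225 − 224 = 1 |

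The weekday labels on the pouches suggest the new-pouch-each-day pattern. Counting baseline as Day 1 gives 13 and 27 days of use, which changes the first two rows only slightly: 3 to 13 (52 used; 11 pouches hold 55) and 2 to 27 (108 used; 22 pouches hold 110).

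The spares may be a buffer for the visit windows. 140 / 4 = 35 days, which is Day 28 + 7. 280 / 4 = 70 days, which is about Day 84 + 14. At a latest-window visit the count can therefore fall to 0.

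**The case against.** The strongest reply is that the design expects some people to know the arm and keeps them apart from the grader. The unmasked designee does accountability and compliance, and there is an unmasked monitor. A leak then needs a departure from procedure or a patient who volunteers a colour. The route to the primary endpoint is also narrow: Day 14 is the only visit between dispensing and the Day 28 grading, and neither Table 3 nor 9.3 schedules container collection there. Nothing says that spare units come back loose rather than in their pouch or box, and the counts above are not exposures. The reference in 8.3 and 8.4 to the investigator or a designee can be read together with 8.5. Instructions to patients may sit in the patient information, which was not examined.

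Much of this stands. Exposure is possible, not required, and its frequency is unknown. The Day 14 route depends on the general rule that containers come to each visit, or on conversation. But none of these points gives a reason for two colours, and none changes the fact that one glimpse or one remark is enough. Role separation controls what staff do. It does not control what a patient carries in or says.

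**Conclusion.** The point holds. The labelling text works against the masking that 7.8 requires, and existing procedures reduce the leak without closing it. The size and direction of any bias cannot be derived from the protocol, and none is claimed. The unit counts show opportunity only, under the stated assumptions of full compliance, on-time visits and one unit per instillation. This is a worthwhile, inexpensive correction to the design, not a demonstrated failure of the primary analysis. The conclusion on colour does not depend on the counts.

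**What to change.** **Main change, section 8.2.3:** put one identical blank sticker, same colour and size, on both products.

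**Secondary wording edits:**
- In 8.3, 8.4 and the Principal Investigator return sentence of 8.5, name the unmasked designee that 8.5 and 8.6 already require.
- State that this person neither grades staining nor gives the investigator's global rating, and receives brought-in containers before the patient meets the grader. List that step first in 9.3 to 9.5. At Day 14 the containers should only be held and handed back, because the patient needs the supply until Day 28.
- Ask patients not to show or describe the containers to the grader, if the patient information does not already say so.

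**Cost:** one sticker colour instead of two, protocol wording, a short container-receipt step at each follow-up visit, and relabelling if units already carry stickers. No new role is needed. The limit is that identical stickers leave masking incomplete if the bare containers differ in appearance, which the protocol text does not say.
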